5.3 Exploratory Efficacy Variables

All exploratory efficacy analyses will be performed based on the observed cases in the FAS population.

 Frequency of preservative free artificial tears use (drops/day) during the follow up period

The number of doses of artificial tears used by patients during the follow-up period will be based on the number of used vials recorded in the artificial tears accountability log, and will be summarized as a continuous variable.

• Change from baseline structural nerve regeneration per confocal microscopy

The confocal microscopy images will be examined by an external reading center to be determined, and will be summarized as a continuous variable.

• Change from baseline in epithelial thickness per anterior segment OCT

Exploratory analysis of anterior segment OCT data will be and will be summarized as a continuous variable.

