Following the completion of the treatment period, patients will be followed up for an additional 24 weeks (for patients healed and non-healed [and not meeting discontinuation criteria] at Week 8) and will be evaluated at the end of the follow-up period. At the investigator's discretion, the subject may be seen for an Unscheduled Visit to evaluate for safety. Patients who prematurely discontinue for whatever reason will not be followed post discontinuation and should have Visit 6 assessments completed.

At Visit 1, eligible patients will be instructed to discontinue all topical ophthalmic medications and will only be allowed to use commercially available preservative-free artificial tears provided by the sponsor to be used up to four times per day during the screening period. At the conclusion of the Baseline Visit (Visit 2) eligible patients will be dispensed a 2-week supply of Study Product from the onsite freezer in a sealed bag and will be instructed to self-administer the Study Product one drop six times a day starting on the day after Day 0/ Visit 2 through Week 8 of the controlled treatment period.

A two week supply of study product will additionally be dispensed to the patients during the treatment period at Visits 3, 4 and 5/Weeks 2, 4 and 6.

Starting from Visit 2, only the study product will be allowed. Preservative free AT provided by the sponsor *will not* be used during the study product treatment period. After the 8 weeks of study product treatment, and during the follow up period, AT should be used only if strictly needed. The use of AT will be tracked in the daily dosing diary.

At Visit 6 (End of Treatment), patients will be assessed for corneal healing.

Rescue Therapy: Commercially available preservative free artificial tears (AT) provided by Sponsor are not allowed during the treatment period. Per the investigators discretion if the patient requires rescue therapy during the 8-week treatment period then they can receive artificial tears provided by the sponsor up to four times per day. The frequency of rescue therapy must be documented in the patient's diary.

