2. SCHEDULE OF EVALUATIONS

	Visit 1	Visit 2	Visit 3	Visit 4	Visit 5	Visit 6	Visit 7
	Day	Day 0	Day 14	Day 28	Day 42	Day 56	Day 224
	(-14)	(±2)	(-2)	(-2)	(-2)	(-4)	(±7)
	Week -2		Week 2	Week 4	Week 6	Week 8	Week 32
Procedures	Screening	Baseline	Product Pick-Up	Treatment Follow-Up	Product Pick-Up	End of Treatme nt	Follow-up/ End of Study
ICF/HIPAA	X						
Demographics, Systemic and Ocular Medical History	X						
Collect date of Stage 1 NK initial diagnosis	X						
Pregnancy Test	X	X				X	
Record AEs	X	X	X	X	X	X	X
Concomitant Medications	X	X	X	X	X	X	X
IDEEL		X		X		X	X
EQ-5D-5L		X		X		X	X
BCDVA	X	X		X		X	X
External Ocular Examination	X	X		X		X	X
Slit Lamp Examination	X	X		X		X	X
Corneal Photography Without Fluorescein	X	X		X		X	X
TFBUT		X		X		X	X
FCS (NEI Scale)	X	X		X		X	X
Corneal Photography with Fluorescein	X	X		X		X	X
Corneal Sensitivity Testing	X	X		X		X	X
Schirmer Test (w/o Anesthesia)		X		X		X	X
IOP	X	X				X	X
Anterior Segment OCT (selected sites)		X				X	X
Confocal microscopy (selected sites)		X				X	X
Inclusion/Exclusion Criteria	X	X					
Assigned to Treatment		X					
Product Dispensation		X	X	X	X		
Collect Used/Unused Study Product			X	X	X	X	
AT Dispensation	X	-				X	
Dispense Daily Dosing Diary	X	X	X	X	X	X	
Evaluate Daily Dosing Diary			X	X	X	X	
Evaluate AT Use- in patient daily diary		X					X

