3.3. OVERALL STUDY DESIGN

This clinical study will be a multi-center, open label, prospective study of 8 weeks of treatment with 24 weeks of follow-up to evaluate the safety and efficacy of OXERVATE[™] 0.002% (20 mcg/mL) cenegermin-bkbj ophthalmic solution administered as one drop in the affected eye(s), 6 times per day at 2-hour intervals, for eight weeks in patients with Stage 1 Neurotrophic Keratitis (NK).

The study is divided into four phases as follows:

- 5. Screening Visit (Day -14): Procedures for inclusion will be performed at both Visit 1 (Screening) and Visit 2 (Baseline). Commercially available artificial tears (AT) provided by the sponsor will be permitted during the Screening period as needed up to four times a day.
- 6. Washout period (from day minus 14 to day 0): 14 days with no further treatment except commercially available preservative-free artificial tears provided by the sponsor. (Note: Xiidra™ and Restasis™ use is disallowed for 14 days prior to Visit 2.) Artificial tears (AT) provided by the sponsor will be permitted up to four times a day and will be tracked via daily diary during washout period.

7. **Treatment:**

- a. Treatment (weeks 1-8): eligible patients will start OXERVATE[™] 0.002% (20 mcg/mL) cenegermin-bkbj ophthalmic solution administered as one drop in the affected eye(s), 6 times per day at 2-hour intervals, for eight weeks. During the treatment period, only study product will be permitted for topical ocular treatment. *Commercially available preservative free artificial tears (AT) provided by Sponsor are not allowed during the treatment period.*
- 8. **Follow up (weeks 9-32):** For the 24 weeks post treatment:
 - a. For patients completely healed, no treatment is allowed except for commercially available AT provided by the Sponsor, administered at the physician's discretion. The use of artificial tears will be tracked via a daily dosing diary.
 - b. For patients not completely healed and who don't meet criteria for premature discontinuation, will also be followed up but any treatment is allowed at the discretion of the physician. All treatment will be tracked as concomitant medications.

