5.2. DOSE, ROUTE AND SCHEDULE OF PRODUCT ADMINISTRATION

Both OXERVATE[™] 0.002% (20 mcg/mL) cenegermin-bkbj ophthalmic solution (study product) and SYSTANE Original[®] (to be used for the screening and follow-up periods only) are to be used in this study and are for topical ocular usage only.

The Study Product will be dosed one drop (35 μ l- .70 μ g of cenegermin-bkbj/drop) 6 times a day in the affected eye(s) for 8 weeks of treatment. The timing of instillation should be adjusted if a patient's awakening and/or bedtime differs based on the suggestion above in Table 1 Dosing Schedule. An example of Dosing Instructions is also provided in the Manual of Procedures (MOP).

Instructions for First Dose:

Patients will be instructed to self-administer the study product one drop in the affected eye(s) six times a day at 2 hour intervals starting on the day after Visit 2 (Day 0-Baseline and First Study product Pick Up) of the treatment period. On Day 1, the patient will start the first dose following Table 1 Dosing Schedule. *The patient should not start therapy on the same day as Day 0/Visit 2.*

On the day of Visit 3/Week 2 (For Study Product Pick-Up), the Study Product dosed is to be instilled in the clinic by the patient at approximately 2 hours intervals according to their established daily schedule for self-administration of the study product at home and the Study Product should be taken from the kit which is dispensed at the visit. This to ensure the patient does not miss a dose during the drop off and pick up day.

Systane Original[®] (commercially available preservative free artificial tears provided by sponsor) will be used only as strictly needed during the Screening and Follow up periods. The use of Systane Original[®] will be clearly documented in the patient's study dosing diary and in the eCRF.

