- **2. EQ-5D-5L:** This self-administered questionnaire will be completed by the patient before any ophthalmic examination is performed at a given study visit. The EQ-5D is a standardized measure of health status developed by the EuroQol Group in order to provide a simple, generic measure of health for clinical and economic appraisal.
- 3. *Concomitant Ocular and Systemic Medications Update: Record any change from Screening/Visit 1 in concurrent ocular or non-ocular medications including information on all concomitant and previous medications used within the past 14 days before Visit 2.
- 4. *Record AE's
- **5.** *Pregnancy Test: Perform a urine pregnancy test on any female of childbearing potential and record the results. If a pregnancy test is not required, indicate as not applicable in the eCRF.
- **6. Ophthalmic Examinations:** following examination/procedures will be performed on BOTH EYES unless otherwise specified:
 - a. BCDVA
 - b. External Ocular Examination
 - c. Slit Lamp Examination
 - d. Corneal Photo Without Fluorescein
 - e. Instill Fluorescein
 - f. Tear Film Break-Up Time (TFBUT)
 - g. Corneal Fluorescein Staining: Using NEI scale (0 to 3 is used for each of the five areas per cornea).
 - h. Corneal Photo with Fluorescein
 - i. Wait 10 minutes before performing Schirmer Test
 - j. Corneal Sensitivity
 - k. Schirmer Test Without Anesthesia (Schirmer I)
 - l. IOP
 - m. Anterior Segment OCT (selected sites)

- n. Confocal microscopy (selected sites)
- 7. Inclusion/Exclusion: Patients must continue to meet the Screening/Enrollment Criteria. At the end of the Baseline Visit (Day 0), it will be determined if the subject qualifies for continued participation and treatment in the study.
- **8. Study Product Dispensing:** Eligible patients will be supplied with a biweekly kit of Study product sufficient for 2 weeks of treatment per visit.
- 9. *Dispense Daily Study Dosing Diary
- 10. Collect used/unused AT and collect/review AT dosing diary
- 11. *Instructions to Subject: Instruct the subject to initiate dosing the study eye or *bilaterally* (if applicable) the following day and to return to the clinic for Visit 3/Week 2 Visit in 2 weeks (14 days). Further instruct the subject to return to the clinic with the Daily Study Dosing Diary and all the empty used/unused daily kit of Study product in the original carton box. Also, remind subject that Systane®, nor any other topical ocular medications), are allowed during study product treatment period.

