carton. Patients should be instructed to try and complete therapy before last treatment appointment, so at time of end of treatment evaluation the patient should have completed the six times a day dosing on Day 56/Week 8 for Visit 6. This will require PIs and their staff to try and schedule the last visit at the end of the day, so the patient has sufficient time to complete 6 doses on the day of Visit 6.

- 6.1.6. Visit 6 (Day 56/Week 8 4 days): END OF TREATMENT OR PREMATURE DISCONTINUATION VISIT
 - 1. IDEEL
 - 2. EQ-5D-5L
 - 3. *Pregnancy Test for women of childbearing potential: Perform a urine pregnancy test and record the results
 - 4. *Concomitant Ocular and Systemic Medications Update
 - 5. *Record AE's
 - **6. Ophthalmic Examinations:** The following examination/procedures will be performed on BOTH EYES unless otherwise specified:
 - a. BCDVA
 - b. External Ocular Examination
 - c. Slit Lamp Examination
 - d. Corneal Photo Without Fluorescein
 - e. Instill Fluorescein
 - f. TFBUT
 - g. Corneal Fluorescein Staining
 - h. Corneal Photo with Fluorescein
 - i. Wait 10 minutes before performing Schirmer Test
 - j. Corneal Sensitivity
 - k. Schirmer Test Without Anesthesia (Schirmer I)
 - l. IOP
 - m. Anterior Segment OCT (selected sites)

- n. Confocal Microscopy (selected sites)
- 7. Collect used Study Product and Subject Dosing Diary
- 8. Dispense Daily Study Dosing Diary
- 9. Dispense Systane®
- 6.1.7. Visit 7 (Day 224/Week 32 ±7 days): FOLLOW-UP/FINAL STUDY VISIT
 - 1. IDEEL
 - 2. EQ-5D-5L
 - 3. *Concomitant Ocular and Systemic Medications Update
 - 4. *Record AE's
 - **5. Ophthalmic Examinations**. The following examination/procedures will be performed on BOTH EYES unless otherwise specified:
 - a. BCDVA
 - b. External Ocular Examination
 - c. Slit Lamp Examination
 - d. Corneal Photo Without Fluorescein
 - e. Instill Fluorescein
 - f. TFBUT
 - g. Corneal Fluorescein Staining
 - h. Corneal Photo with Fluorescein
 - i. Wait 10 minutes before performing Schirmer Test
 - j. Corneal Sensitivity
 - k. Schirmer Test Without Anesthesia (Schirmer I)
 - l. IOP
 - m. Anterior Segment OCT (selected sites)
 - n. Confocal Microscopy (selected sites)

- 6. *Collect Daily Study Dosing Diary
- 7. Patient will be discharged from the study

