7.1.2. Exploratory Efficacy Endpoints

1. Frequency of preservative free artificial tears use (n° drops/day) during the follow up period.

At selected sites:

The following may be evaluated as part of a post-hoc analysis:

- **2.** Change from baseline structural nerve regeneration (density, length, nerve density, tortuosity) per confocal microscopy.
- **3.** Change from baseline in epithelial thickness per anterior segment OCT.

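### SAP 5.3 heads follow-up artificial-tear use as drops/day but derives an undivided count of used vials, from a log that no listed Visit 7 step feeds

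*SAP*

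**What the plan says.** **The endpoint.** Protocol 7.1.2 lists "Frequency of preservative free artificial tears use (n° drops/day) during the follow up period". SAP 5.3 repeats it under a drops/day heading.

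**The derivation.** Under that heading, SAP 5.3 takes the number of doses used by patients in follow-up, says it "will be based on the number of used vials recorded in the artificial tears accountability log", and summarises the result as a continuous variable.

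**Where use is recorded.** Protocol section 1 (Synopsis) states: "The use of AT will be tracked in the daily dosing diary". Protocol 3.3 repeats this. Protocol 5.2 says artificial-tear use is documented in the patient's "study dosing diary and in the eCRF". In the Schedule of Evaluations (Protocol section 2), the artificial-tear row marked at Visits 2 and 7 reads "Evaluate AT Use- in patient daily diary".

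**What the visits list.**
- Visit 2 (Protocol 6.1.2): "Collect used/unused AT and collect/review AT dosing diary".
- Visit 6 (Protocol 6.1.6): a diary and artificial tears are dispensed.
- Visit 7 (Protocol 6.1.7): "Collect Daily Study Dosing Diary", with no return or count of artificial-tear containers.

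**Analysis set.** SAP 5.3 places exploratory analyses on observed cases in the Full Analysis Set. SAP Appendix 2 assigns Table 14.2.9, on follow-up artificial-tear exposure, to the Full Treated Set.

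**The concern.** The derivation does not deliver the unit in its own heading. Three things are missing or unsettled.

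1. **Conversion.** Nothing says how many drops one used vial represents. Even the container is not settled: Protocol 6.1.1 speaks of bottles, the SAP of vials.
2. **Denominator.** No division by days is stated. Patients who meet the deterioration or no-improvement definition during follow-up are discontinued (Protocol section 1 and 3.3), so time at risk differs between patients.
3. **Supply of data.** No listed step at Visit 7 feeds the log for the follow-up period. Patients who leave early complete Visit 6 procedures (Protocol 6.2), and these list no artificial-tear return either.

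At stake is whether the reported figure can be read as need for lubrication after treatment. A programmer following SAP 5.3 literally would report a container count under a drops/day label.

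**Working it through.** The plan states no figure for this endpoint, so there is nothing to reproduce. The check is one of units and data flow.

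**Inputs from the documents**
- End of treatment: Day 56, window −4 days. Final visit: Day 224, window ±7 days (Protocol section 2).
- Nominal follow-up: 224 − 56 = 168 days. Shortest: 217 − 56 = 161. Longest: 231 − 52 = 179.

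**Assumed, because the documents do not say**
- 168 used vials in total, and 1, 2, 4 or 10 drops per vial.

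**Step 1: conversion.** Drops/day = vials × drops per vial ÷ days.

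| Drops per vial | 161 days | 168 days | 179 days |
|---|---|---|---|
| 1 | 1.04 | 1.0 | 0.94 |
| 2 | 2.09 | 2.0 | 1.88 |
| 4 | 4.17 | 4.0 | 3.75 |
| 10 | 10.43 | 10.0 | 9.39 |

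The visit windows hardly matter. The conversion decides the answer. Even if one vial is one dose, and a dose is one drop per eye, 168 vials mean 1.0 drop/day for use in one eye and 2.0 for use in both. Protocol 4.3 allows bilateral treatment with study product, so two-eye use is a realistic case.

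**Step 2: denominator.** Take two patients who each use one vial a day. One stays 168 days and the other is discontinued at day 84 of follow-up (assumed). Their counts are 168 and 84, although their frequency is the same. Conversely, 168 vials used in 84 days is 168 ÷ 84 = 2.0 vials/day, against 168 ÷ 168 = 1.0 for a completer with the same count. The undivided count would rank the first pair as different and the second pair as equal. Both rankings are wrong for a frequency endpoint.

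**Step 3: data flow.** Visit 2 lists collection of both containers and diary. Visit 7 lists the diary only, and the Visit 7 schedule row is diary-based. The diary therefore has a listed route to the database at the end of follow-up. The container count has none. The share of containers not returned is unknown, so no size can be put on this part.

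**Secondary: SAP 4.3.** Washout artificial-tear use is reported as last date minus first date plus one, labelled as days of use. With use on days 1, 3, …, 13 (assumed), the span is 13 − 1 + 1 = 13 days, while days with use number 7; 13 ÷ 7 = 1.86.

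**The case against.** **The log is a planned record.** Protocol 12.1 has monitors assess accountability of the concomitant study product, and SAP Appendix 2 includes an artificial-tears accountability listing (16.2.5.4). The Manual of Procedures is not available here and may cover container returns. This stands. It would be wrong to say that the log does not exist or is known to be incomplete. The documents show only that no listed Visit 7 step supplies it. A complete log would still give neither a conversion nor a denominator.

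**The unit may be settled in the mock shells.** SAP section 1 describes these as a separate working document. That is possible, but SAP 5.3 is where the derivation is defined, and the listed title of Table 14.2.9 carries no unit.

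**The follow-up period is fixed.** For completers this is nearly right: at one drop per vial the windows move the result only between 0.94 and 1.04. It does not help for patients discontinued during follow-up.

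**A reader might infer a breach of the protocol.** The documents do not support that. The protocol says where use is recorded but names no analysis source for this endpoint, and SAP section 1 says the SAP supersedes the protocol's statistical considerations.

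**A reader might also infer that the diary covers only healed patients.** Protocol 3.3 does say "The use of artificial tears will be tracked via a daily dosing diary" under completely healed patients, and treatments for the others go to the concomitant medication log. However, Visits 6 and 7 dispense and collect the diary without reference to healing status, and the other diary statements in Protocol 3.3 and 5.2 are equally unrestricted. Restricting the endpoint to healed patients would condition on a post-treatment outcome and depart from the Full Analysis Set basis.

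**The SAP 4.3 span is openly defined** and follows the same convention as exposure in SAP 4.4. That is fair. But artificial tears in washout are taken as needed, whereas study product is dosed daily, so the span suits one and not the other.

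**Conclusion.** The point holds as a minor one. SAP 5.3 as written gives an undivided container count under a drops/day heading. The unit and denominator problems follow from the text alone. Possible incompleteness of the log is a risk inferred from the visit lists, not an established fact.

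The size depends on assumptions. The implied rate scales directly with drops per vial (1.0 to 10.0 drops/day over the range shown), and discontinuation halfway through follow-up changes the meaning of a given count by a factor of two. No estimate of actual bias is possible from the documents.

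The effect is confined to one exploratory descriptive endpoint, with the washout summary in SAP 4.3 as an optional tidy-up. No healing or safety conclusion changes.

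**What to change.** **In SAP 5.3**
- Define drops/day per patient as total artificial-tear drops recorded in the follow-up diary, divided by follow-up diary days up to Visit 7 or discontinuation. State that drops in two eyes are both counted.
- Show the result twice: with blank diary days excluded, and with blank days counted as no use.
- Keep every patient with diary data, whatever the healing status at Week 8.
- Use the accountability log as a cross-check only.
- Reconcile the analysis set between SAP 5.3 and Table 14.2.9.

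**If the log is kept as the source instead,** SAP 5.3 needs a vial-to-drop rule and a day denominator, and Visit 7 needs a container return and count.

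**Optional, SAP 4.3:** report the number of washout diary days with artificial-tear use.

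**Cost.** The diary route is mainly SAP wording and programming, since the diary is already dispensed at Visit 6 and collected at Visit 7. It has two drawbacks. Blank days over 24 weeks are ambiguous: with 20% blank and 2 drops on recorded days (both assumed), the two versions give 2.0 and 2 × 0.8 = 1.6 drops/day. Daily counts must also reach the eCRF. Protocol 5.2 says use is documented there but not as drops per day, so the form should be checked. Keeping the log costs more, because it adds a visit procedure.

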5.4 Methods of Efficacy Analysis

Descriptive statistics of the observed and change from baseline of each continuous efficacy endpoint described above will be tabulated by visit where that endpoint is assessed. Where appropriate, the asymptotic 95% confidence intervals of mean change from baseline will be presented.

Analyses for responder/categorical endpoints such as percentage of patients who experience epithelial healing at 4 and 8 weeks, and percentage of patients who remain healed throughout the follow-up period will include percentage of response, and associated exact (Clopper-Pearson) 95% confidence intervals where appropriate.

All efficacy results will be tabulated based on both FAS and FTS as appropriate.

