9.1. SAMPLE SIZE

A sample size of 35 evaluable patients (patients completing 8 weeks of OxervateTM) will achieve a lower limit of 95% confidence interval equal to 40% and 54% when the percentage of subjects who experience epithelial healing is 58% (at 4-week) and 72% (at 8-week), respectively.

The sample size calculation was based on previous trial calculations from NGF0212 (REPARO) and NGF0214 (US trial) that showed statistical superiority in complete healing after 8 weeks of treatment with cenegermin, 72% and 65.5% respectively. Assumption for this target, has been proportion of patients achieving complete healing of staining (grade 1 or less on NEI scale) by week 8.

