9.3.2. Analysis of efficacy variables

Analyses for responder outcomes will include percentage of response and exact 95% confidence intervals. Analyses of change from baseline and continuous outcomes will include mean and associated asymptotic 95% confidence intervals. No formal hypothesis test will be conducted.

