5.2 Secondary Efficacy Variables

All the analyses of secondary efficacy variables will be performed based on the observed cases in the FAS population. No missing data imputation will be considered.

• Percentage of patients who experienced epithelial healing at 4 weeks

The patients who experienced epithelial healing at Visit 4/Week 4 will be determined for study eye similarly as the primary efficacy variable. It will be summarized as a binary goal attainment variable (Yes/No).

• Percentage of patients who achieved epithelial healing at Week 8 and remained healed throughout the follow-up period

The patients who achieved epithelial healing at Week 8 and remained healed throughout the follow-up period will be determined for study eye at Visit 7/Week 32 similarly as the primary efficacy variable. It will be summarized as a binary goal attainment variable (Yes/No) based on the subset of patients who achieved epithelial healing at Week 8, as well as based on the FTS.

• Percentage of patients who experienced complete healing at Week 4 and 8

The patients who experienced complete healing at Week 4 and 8 will be determined for study eye by the investigator and recorded on eCRF. The complete healing is defined as Grade \leq 1 in the central qualifying zone of study eye via FCS (per NEI scale) and no persistent staining in the non-qualifying zones (excluding the superior zone) defined as the absence (Grade 0) of pathological staining via corneal photography. It will be summarized as a binary goal attainment variable (Yes/No).

• Percentage of patients who achieved complete healing at Week 8 and remained completely healed throughout the follow-up period

The patients who achieved complete healing at Week 8 and remained healed throughout the follow-up period will be determined for study eye at Visit 7/Week 32 by the investigator and recorded on eCRF. It will be summarized as a binary goal attainment variable (Yes/No) based on the subset of patients who achieved complete healing at Week 8, as well as based on the FTS.

• Mean change in corneal sensitivity from baseline at 4, 8, and 32 weeks

The corneal sensitivity (cm) in the NEI zone of the study eye as measured by the Cochet-Bonnet aesthesiometer will be summarized as a continuous variable.

• Percentage of patients that achieve an improvement in corneal sensitivity at 4, 8, and 32 weeks

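### SAP 5.4 asks for asymptotic intervals for mean changes with about 35 patients; read as ±1.96 SE they are slightly too narrow, and a t interval corrects this under normality

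*SAP*

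**What the plan says.** SAP 5.4 covers intervals for continuous endpoints in one sentence. It opens with the condition that this be appropriate, and continues: "the asymptotic 95% confidence intervals of mean change from baseline will be presented". Protocol 9.3.2 has the same method without the opening condition: "Analyses of change from baseline and continuous outcomes will include mean and associated asymptotic 95% confidence intervals". For responder endpoints SAP 5.4 instead specifies "associated exact (Clopper-Pearson) 95% confidence intervals where appropriate", and Protocol 9.3.2 also calls for exact intervals there. Neither document says whether the multiplier for means is a normal or a t quantile.

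The continuous endpoints are in SAP 5.2: corneal sensitivity in cm, Schirmer, TFBUT, BCDVA in logMAR, the IDEEL subscores and the EQ-5D-5L scores. On the data to be used, that section says: "All the analyses of secondary efficacy variables will be performed based on the observed cases in the FAS population". Missing values are not imputed.

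The planned size in Protocol 9.1 is 35 patients who complete 8 weeks of treatment. Protocol 9.3.2 plans no hypothesis test, and SAP 2.10 treats every efficacy analysis as exploratory. SAP Section 1 says that the SAP overrides the protocol on statistical matters.

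**The concern.** The plan protects proportions against small-sample error by using exact intervals, but names a large-sample method for means at the same sample size. An interval of mean ± 1.96 SE treats the estimated standard deviation as known. It is therefore narrower than its nominal level requires at any finite n, so the error always overstates precision.

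With no test planned, these intervals are the only statement of uncertainty for Schirmer, TFBUT, IDEEL and EQ-5D-5L. The plan's own rules can also reduce some denominators:

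- **Week 32.** Patients who meet the deterioration or no-improvement definition at Week 8 leave the study (Protocol 3.3), and patients lost during follow-up are not replaced (Protocol 6.2).
- **IDEEL Work.** The items are set to missing for anyone not currently working (SAP 5.2, Module 1.c), and a change score needs a value at both visits.

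**Working it through.** **1. The plan's own precision figure.** Protocol 9.1 says that 35 patients "will achieve a lower limit of 95% confidence interval equal to 40% and 54" percent, when the percentage who "experience epithelial healing is 58% (at 4-week) and 72% (at 8-week), respectively". The exact two-sided lower limit is the 0.025 quantile of Beta(x, n − x + 1) with x = n·p.

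- Week 4: x = 35 × 0.58 = 20.3, lower limit 40.2%.
- Week 8: x = 35 × 0.72 = 25.2, lower limit 54.3%.

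Both match the stated 40% and 54%. Other methods do not match both: Wald gives 41.6% and 57.1%, Wald with continuity correction 40.2% and 55.7%, Wilson 41.7% and 55.5%. Whole-number counts of 20 and 25 give exact limits of 39.4% and 53.7%. The sample-size statement thus rests on the exact method for proportions and is not affected by this point.

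**2. Intervals for means.** Inputs: two-sided 95% level, z = 1.960, and n. Only n = 35 comes from the documents; the other values are assumptions to show the range. No standard deviation is needed, because it cancels.

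- Shortfall in width = 1 − 1.960 / t(0.975; n−1).
- Actual coverage of mean ± 1.960·SD/√n with normal data = 2·T(1.960; n−1) − 1, where T is the t distribution function.

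At n = 35, t(0.975; 34) = 2.0322. The shortfall is 1 − 1.9600/2.0322 = 3.6% and coverage is 94.2%. In SD units the half-width is 1.960/√35 = 0.331 with z and 2.0322/√35 = 0.344 with t.

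| n | t multiplier | z interval too narrow by | Coverage of z interval |
|---|---|---|---|
| 45 (assumed) | 2.015 | 2.8% | 94.4% |
| 40 (assumed) | 2.023 | 3.1% | 94.3% |
| 35 (planned) | 2.032 | 3.6% | 94.2% |
| 30 (assumed) | 2.045 | 4.2% | 94.0% |
| 20 (assumed) | 2.093 | 6.4% | 93.5% |
| 15 (assumed) | 2.145 | 8.6% | 93.0% |
| 10 (assumed) | 2.262 | 13.4% | 91.8% |

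**3. What t does not repair.** The table assumes normal data. A simulation of 200,000 samples per n, with strongly skewed changes (lognormal with log-scale SD 1, an assumption), gave at n = 35 a coverage of 87.9% with z and 88.8% with t. At n = 10 it gave 80.6% and 83.9%. With skewness of that degree, the shape of the data matters more than the multiplier.

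**The case against.** The strongest reply is that the documents never write normal, z or 1.96, so the plan has left a detail open and has made no error. This stands in part: the size of the problem is conditional on the usual reading. But asymptotic is set directly against exact for proportions, and the t interval is a finite-sample method. If the programming returned t limits, they would be sound under normality but would not be what the plan describes.

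Second, the SAP sentence is conditional, and the SAP governs. The condition could let the sponsor omit an interval in a very small group. It does not change how an interval is computed when one is shown, and no criterion for applying it is given.

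A reader might also infer stronger points, which the documents do not support:

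- **That every mean-change interval is certainly too narrow.** The multiplier is not stated and the SAP wording is conditional.
- **That n is at most 35 and often far lower.** The 35 counts 8-week completers. The Full Analysis Set needs only a single dose (SAP 2.6.3), and early discontinuers are replaced (Protocol 6.2), so n at Weeks 4 and 8 can exceed 35. The routes to smaller groups are documented, but their sizes are not.
- **That these intervals are the only inference for every continuous measure.** Corneal sensitivity and BCDVA also have responder endpoints (any improvement, 15-letter gain) with exact intervals.
- **That imaging is the prime example.** Protocol 7.1.2 leaves OCT and confocal analysis as a post-hoc possibility. SAP 5.3 plans summaries, but SAP Appendix 2 lists no imaging output.

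Finally, t limits assume normality, while EQ-5D-5L dimensions run from 1 to 5 and IDEEL scales are bounded. That limits what the fix achieves; it is no reason to prefer z.

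**Conclusion.** The point holds and is minor. The named method, read in the usual way, is slightly too optimistic about precision: under one percentage point of coverage at the planned 35 patients, and more in any group that turns out much smaller. It becomes material only at around 10 patients or fewer, and whether any analysis gets that low cannot be determined from the documents.

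This rests on two assumptions: that asymptotic means a normal multiplier, and that the changes are roughly normal. No success criterion depends on these intervals, and the primary result at Week 8 is untouched.

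**What to change.** In SAP 5.4, replace the word asymptotic with t-based (n−1 degrees of freedom). SAP 2.9 already lists the number of observations among the descriptive statistics; state that n for the change score is printed beside each interval, for every visit and every IDEEL domain, so that small groups are visible. Record the departure from Protocol 9.3.2 in SAP Section 9, which now says that none is planned.

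A protocol amendment is not needed for this alone, because the SAP takes precedence on statistics. The cost is one SAP revision and slightly wider intervals: 2.0322/1.9600 = 1.037, or 3.7% wider at n = 35. The change does not correct for skewness, so intervals for clearly skewed or bounded scores should still be read alongside the medians and ranges already planned in SAP 2.9.
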